	4.2 Patient Consent		
	Appendix 1: Schedule of Study Procedures		
	Appendix 2: Clinical Laboratory Tests	18	
	Appendix 3: Investigator Obligations	19	

Version Date: 1/13/2021 v9

List of Abbreviations and Definition of Terms

Abbreviation	Definition					
AE	Adverse event					
AEMG	Adverse event management group					
AIDS	Acquired immunodeficiency syndrome					
ALT	Alanine transaminase					
ANOVA	Analysis of variance					
AST	Aspartate transaminase					
BSS	Bismuth subsalicylate					
BID	Twice daily					
FCALP	Fecal calprotectin					
CFR	Code of Federal Regulations					
COX	Cyclo-oxygenase					
CQA	Clinical Quality Assurance					
CRP	C-reactive protein					
CT	Computed axial tomography					
COV+	COVID+ patient					
eCRF	Electronic case report form					
ER	Emergency room					
ERES	Electronic Records/Electronic Signatures					
ESR	Erythrocyte sedimentation rate					
FCALP	Fecal calprotectin					
FDA	Food and Drug Administration					
GCP	Good Clinical Practice					
GI	Gastrointestinal					
GSS	Global symptom score					
HIV	Human immunodeficiency virus					
HQUANT	Hemoquant assay					
ICF	Informed consent form					
ICH	International Conference on Harmonization					
IEC	Independent Ethics Committee					
IgA	Immunoglobulin A					

IL Interleukin

IM Intramuscular

IRAE Immediately reportable adverse event

IRB Institutional Review Board

ITT Intent-to-treat
IV Intravenous

IVRS Interactive voice response system

LF Lactoferrin

MCH Mean corpuscular hemoglobin

MCHC Mean corpuscular hemoglobin concentration

MCV Mean corpuscular volume

NO Nitric oxide

NSAID Nonsteroidal anti-inflammatory drug

PMNs Polymorphonuclear elastase

PO Oral

POC Proof of concept SOC Standard of Care

TEAE Treatment-emergent adverse event

TD Traveller's diarrhea

US United States

WBC White blood cell count

Clinical Protocol Body

1. Study Rationale/Background

The CDC and WHO have deemed the COVID-19 virus a global pandemic of unprecedented severity in modern times. In 2019, this novel Coronavirus (COVID-19) emerged from the Asian continent and has now caused upwards of 360,000 deaths and over 6 million infections globally. Its impacts economically and socially are massive, with an estimated global economic impact of over 5 Trillion dollars.

Understanding the host response to pathogens, specifically the cellular and humoral responses, has played an important role in new non-antibiotic therapies.

Scientific understanding of immune characteristics of virus susceptibility have opened the door to the development of diagnostic and therapeutic agents to identify and treat patients at risk of acquiring COV+, and treating patients at risk of developing persistently positive (by QRT-PCR) COV+ disease or mild COV+ disease.

An extensive epidemiologic study of the mechanism of transmission of the Coronavirus SARS is available on-line. Fauci's textbook, Harrison's Principles and Practise of Infectious disease (2013) outlined the potential of an intestinal nidus of Coronavirus. Viral shedding of Coronavirus was detected up to 2 months following the resolution of respiratory infection in some individuals. This further emphasizes the gut involvement of this class of viruses and the interest in determining the causative and treatment opportunities afforded by a gut-focused strategy to decreasing viral load and shedding. Further, GI symptoms have been found in a significant number of patients with COVID-19, although the incidence of these symptoms vary immensely by region studied.

An IND is not needed for this study as we are primarily looking at stool frequency.

Bismuth subsalicylate (Pepto-Bismol) has a potential role in the clearance and/or recurrence of non-COV+ enteric viral infections.

Readily available over-the-counter (OTC) medication for symptomatic relief and appropriate oral hydration can be health saving measures of great convenience for those affected by enteric bacterial and viral infections. BSS is a non-proprietary monograph product that is available in the USA and abroad, over-the-counter (OTC). Of all OTC medications for TD, bismuth subsalicylate (BSS) has the greatest antimicrobial activity against pathogenic bacteria. A study by Gump et al. (1992) first demonstrated the ability of BSS to decrease the invasiveness of enteropathic bacteria in gastrointestinal epithelial cells. Electron-dense deposits of bismuth were found in Yersinia enterocolitica cells exposed to BSS. indicating that the antibacterial effect of BSS was mediated by its ability to increase permeability of the bacterial cell wall and increase bismuth concentrations in bacterial cells. Other studies had indicated that the exposure of bacteria to BSS resulted in a loss of membrane integrity and, possibly, inactivation of cellular ATP synthesis leading to death of the organism. More recently, Pitz et al. (2015) verified in vitro the antimicrobial effects of BSS and bismuth oxychloride (BiOCl) on key pathogens, such as Escherichia coli O104:H21 (surrogate to 2011 German outbreak strain), Salmonella, and norovirus (NoV). These authors showed that bismuth reduced bacterial growth significantly, resulting in less than 10cfu/ml within 24hrs. C. difficile was the most susceptible pathogen to the bismuth challenges in the antibacterial assays. BSS also exhibited significant inhibition on viral invasion of host cells and viral efficacy. Both BSS and bismuth oxychloride (BiOCl, which is formed in the stomach after ingestion of BSS) at low concentration (0.004-0.13mg/mL) significantly reduced NoV RNA levels. suggesting an in vivo antiviral mechanism. BSS has also been shown to have antiviral activity since it

inhibited replication of 4 strains of rotavirus in tissue culture cells and caused a dose-dependent reduction in the growth of several enteric viruses.

Historically, BSS has been indicated and effectively used for the treatment of TD or enteric infection, mainly when vomiting occurs. Although the safety and efficacy of BSS is well known, some of the research done with BSS resides within the industry and have not been published. I have recently completed an extensive meta-analysis using unpublished clinical studies regarding BSS safety and efficacy. Meta-analyses of randomized controlled clinical trials were performed with studies specifically designed to capture prevention of manifestation and relief of diarrhea.

The first meta-analysis specifically assessed the diarrhea preventive effects of BSS in generally healthy adults who had no diarrhea at the time of randomization. Five P&G-sponsored studies were identified for consideration. Out of the five studies, 3 were designed for prevention of TD, and 2 involved induced diarrhea through viral inoculation (Norwalk agent or Norovirus) or chemical irritation (castor oil consumption) induced diarrhea. Although BSS had shown efficacy in these 2 chemical irritation studies, in order to maintain relevance to populations at risk for TD, only the 3 naturally occurring diarrhea studies were considered for meta-analysis. All 3 studies (n=404 subjects, age between 16 to 70 years old) followed a similar parallel-group, placebo-controlled design in diarrhea-free individuals embarking on a trip to tropical countries (Mexico and African destinations) known for elevated incidence of TD. All subjects initiated a 21-day prophylactic BSS dosing regimen (one study used BSS tablets QID to a total of 2.1g/day, the second study used oral suspension of 1050 mg QID to a total dose of 4.2 g/day and the third study used tablets BID to total dose of 2.1g/day) starting from 1 day before departure or 2 days after arrival at the trip destination.

The meta-analysis efficacy endpoint was self-assessed diarrhea (presence/absence) during the 21-day treatment period. Meta-analysis results are reported in terms of odds ratios and 95% confidence intervals with larger values indicative of greater efficacy for BSS relative to placebo. The data indicate that subjects who dosed BSS had 3.5 times greater odds of not developing TD than subjects who dosed placebo (95% CI: $2.1, 5.9; p < 0.001, I^2 = 27\%$).

Several studies have identified gastrointestinal symptoms associated with COVID-19. Up to 60% of patients in some studies had upper or lower gastrointestinal symptoms, including diarrhea.

Two specific papers have supported the use of Bismuth as a treatment option for COV+. [name] (Hong Kong) found that Bismuth was effective in inhibiting the SARS Corona virus helicase. Of note, this potential efficacy was noted by the Jinyintan Hospital during the current COV-19 pandemic. After several of their staff were infected, they used bismuth compounds prophylactically and noted no further infections.

These data point to the efficacy of preventing viral enteritis and low risk-profile for patients treated with BSS. Clearly, BSS may be part of a strategy for COV+ treatment given its low therapeutic risk profile and documented gut-virus clinical efficacy.

2. Study Objectives

The objectives of this pilot study are: To evaluate the tolerance and efficacy of BSS and SOC in mild/moderate severity COV+ population as defined by QRT-PCR of saliva or nasal swab samples compared to SOC and placebo and compare this efficacy to patients treated with SOC (placebo) alone. This will first be tested in 10 open-label patients, then in 2 groups of 25 patients as follows: Group one with mild/moderate disease and Group 2, patients with mild/moderate disease and persistently positive

for the SARS-Cov-2 virus by QRT-PCR testing for 14 days or more. This study is to assess the potential for BSS to influence the gut as a reservoir of infection by the SARS-Cov-2 virus and to determine the primary effect objective of change in stool frequency of patients treated with BSS compared to placebo treated patients.

Primary efficacy objective:

To determine whether treatment with BSS of Mild/Moderate COV+ decreases mean daily stool frequency compared to placebo-controlled patients

Secondary efficacy objectives:

Duration of hospitalization in BSS compared to PBO treated groups.

Weight gain (and BMI) relative to baseline at Week 1, and through Week 2.

Stool microbiota at baseline and Week 1, and through Week 2 (to be analysed at a later date).

To determine whether treatment with BSS of Mild/Moderate COV+ decreases the time to viral clearance (negative test by daily saliva testing) and persistently COV+ testing patients (over 14 days of COV+ testing) with Mild/Moderate disease, time until negative test by daily Saliva test.

3. Investigational Plan

3.1 Study Design

This will be a 3 week, randomized, single-center, double-blind, proof-of-concept (POC) pilot study to evaluate the efficacy of patients with mild-moderate COVID-19+ infection. There will be an initial 10-pateint open-label study to assess patient tolerance to the active treatment arm of the study. The first 10 open-label patients will be treated with BSS 2 tablets PO (to chew) up to 4 times daily for 3 days (72 hours). The second 2 groups of patients will be mild (at home) or moderate (hospitalized, not on a ventilator) COV+ testing or with persistently + COVID testing for 14 days or more.

Patients will be allowed to receive a SOC treatment regimen at baseline (Appendix 2)

Standard of care (which includes any non-excluded SOC medications).

This pilot study will be conducted in the US in 1 center. A total of 60 patients are expected to be enrolled into the 3 arms of the study. Study one will consist of 10 open label COV+ patients with mild/moderate disease, the second and third studies will be double-blind placebo controlled studies of 25 patients each, the first with Mild/Moderate disease upon diagnosis by QRT-PCR+ testing and the third will consist of patients who are COV+, mild to moderate in severity with documented COV+ status by QRT-PCR testing for 14 days or more.

Screening will occur at the time patients are diagnosed via QRT-PCR testing. This may occur at one of several locations and/or time points of diagnosis:

- emergency room [ER]
- physician's office on the U of L campus.
- · University of Louisville hospitals (ULH Main and Jewish facilities).
- · Selected parking lot on UL campus.

 Campus Health (patients/students may be recruited via Practitioners or by approved recruitment flyers

Patients with initial COV+ confirmed by QRT-PCR testing will be approached to provide informed consent for the study. A third group of patients will be recruited with persistently + QRT-PCR testing for 14 days or more (see table 2).

Randomization will occur during SOC treatment.

Visits will occur at Baseline (Day 1) when patients will receive their first dose of study drug (BSS or PBO), and daily during the study until the patient tests COV- by saliva test or 21 days, whichever comes first.

The study design is depicted in Appendix 2.

3.2 Selection of Study Population

3.2.1 Inclusion Criteria

To be eligible to participate in the study, patients must meet the following criteria:

- Ability to provide written or remote informed consent (telephone and DocuSign)
- Ability to comply with study requirements,
- Men or women 18 to 85 years of age, inclusive
- Current diagnosis of an initial occurrence of non-severe, non-complicated COV+ infection as defined by:
 - Presence COVID-19 in the saliva or nasal cavity using POC QRT-PCR assay or, in study #3, documented COV+ status for 14 days or more.
 - Management in an outpatient (i.e., non-hospital) or inpatient setting NOT on a ventilator.
 - Alert and awake
 - · Able to chew the study drug completely.
 - Women should fulfill one of the following criteria:
 - Answer in the affirmative that "they are not or could not be pregnant"
 - Post-menopausal; either amenorrhea ≥12 months or follicle stimulating hormone >20 mIU/mL
 - Surgically sterile; hysterectomy, bilateral oophorectomy, or tubal ligation.
 - Women of childbearing potential participating in heterosexual sexual relations must be willing to use adequate contraception from Screening through the 21 Day visit, per Section 10.2.

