3.2.2 Exclusion Criteria

Patients with any of the following will be excluded from admission into the study:

- Existence of an intra-abdominal abscess, enteric fistula, or symptomatic bowel obstruction
- History of allergy to salicylates.
- History of short gut syndrome, active ulcer or recent history of GI bleeding or melena.
- Systemic chemotherapy for the treatment of cancer during the 60 days prior to consent or planned during the study

- Presence of ileostomy or colostomy, or history of prior gastric resection or significant colon resection
- Intra-abdominal surgery within the past 60 days
- Current use of drugs that control diarrhea or affect peristalsis (e.g., loperamide. Opiates
 can be used in hospitalized patients and with outpatients if they are prescribed to a
 patient), or any anticipated use during the study
- Active drug, chemical, or alcohol dependency as determined by Investigator through history or urine toxicology screen
- Enrollment in any other investigational drug or device study known to interfere with Pepto bismol (bismuth subsalicylate) within the GI tract, within 30 days prior to Randomization (Day 1) or within 5 half-lives of the last dose of the previous investigational compound, whichever is longer. Vaccines are not exclusionary as they do not interfere with the mechanism of the study drug.
- Severe acute illness unrelated to COVID-19
- · Pregnant, breast-feeding, or considering becoming pregnant during the study
- · Planned hospitalization or surgery during the study
- Any medical, psychiatric, social, or other circumstances that may interfere with study compliance, completion, or accurate assessment of study outcomes

Standard therapy that is used for treatment of COVID-19 infection does not constitute an exclusion from this study.

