3.4.1.1 Screening Visit (Days -1 to 0)

Screening will occur at the time the diagnosis of COV+ is confirmed for the first study. For the second study, screening will occur at 2 weeks or more of documented COV+ status. During the screening visit

enrolled patients will be provided with a stool collection kit. Two patient groups will be studied: The following will be obtained to determine patient eligibility:

- a. Written or remote informed consent; (telephone and DocuSign)
- b. Demographic data;
- c. Medication history for the previous 30 days;
- d. Medical history including daily stool frequency;
- e. Social history (alcohol, tobacco, drugs);
- f. Height and Weight (which can be self-reported);
- g. Vital signs (temperature, pulse, blood oxygen saturation, blood pressure within 1 week of screening visit);
- h. Verbal affirmation that to the best of their knowledge they are not pregnant;
- i. Collection of serious, procedure-related non-treatment emergent AEs;
- Reminder for patients to avoid the use of protocol excluded medications for the duration of the study

All screening laboratory test results must be reviewed, signed, and dated by an Investigator when they are received (see list in Appendix 2).

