3.4.2 Efficacy Assessments

- Mean daily stool frequency and aggregate weekly stool frequency of treated versus placebo treated patients
- Time to negative test of subjects experiencing clinical cure (negative test of saliva-confirmed COV+infection).
- Incidence of Adverse Events (AEs)

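### Stool frequency is the primary objective, but patients enter without raised counts and the baseline count is used in neither allocation nor analysis

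*Combined protocol and SAP*

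**What the plan says.** Section 2 (Study Objectives) states the primary efficacy objective as "To determine whether treatment with BSS of Mild/Moderate COV+ decreases mean daily stool frequency compared to placebo-controlled patients". Section 3.4.2 measures it as "Mean daily stool frequency and aggregate weekly stool frequency of treated versus placebo treated patients". It gives no consistency scale, normal range or responder definition.

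Section 3.2.1 sets the disease criterion as "Current diagnosis of an initial occurrence of non-severe, non-complicated COV+ infection as defined by", followed by "Presence COVID-19 in the saliva or nasal cavity using POC QRT-PCR assay or, in study #3, documented COV+ status for 14 days or more". The remaining criteria cover consent, compliance, age, care setting, alertness, ability to chew, and pregnancy or contraception status. None concerns bowel habit. The related exclusion in section 3.2.2 is "Current use of drugs that control diarrhea or affect peristalsis".

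Section 3.4.1.1 collects "Medical history including daily stool frequency" at screening, and section 3.4.1.2 records stool frequency again on Day 1. Section 3.5.1 assigns patients by coin toss or another suitable method, with no strata. In section 3.6.1 the only named covariate is baseline BMI, attached to the saliva analysis. The methods for continuous endpoints name no covariate.

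On how common symptoms are, section 1 says: "Up to 60% of patients in some studies had upper or lower gastrointestinal symptoms, including diarrhea". It gives no separate figure for diarrhoea and adds that incidence differs widely by region.

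**The concern.** An anti-diarrhoeal effect can show itself only in patients whose stool frequency is raised. If a sizeable share enter with normal counts, three things follow.

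- **Dilution.** The all-patient mean difference shrinks towards zero. The wide spread between patients with and without diarrhoea also inflates the standard error unless baseline is taken into account.
- **Chance imbalance.** With very few placebo patients per cohort and no stratification, the placebo arm may hold few or no patients with raised counts. The comparison then partly reflects who was allocated where.
- **Direction.** On a raw count, a fall from a normal frequency to a low one scores as success. Section 3.4.3 does not count symptoms as adverse events unless they are serious or cause withdrawal, so the safety data would not reliably show the difference either.

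A null result could then be dilution, and a positive one could be hard to interpret as relief of diarrhoea.

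**Working it through.** The documents state no sample-size calculation, effect size, SD or alpha for stool frequency, so there is no planned figure to reproduce. The steps below use the documents' counts and labelled assumptions.

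**1. Expected patients without symptoms.** Inputs: 25 patients in each of two randomised cohorts (section 3.1), and at most 60% with any upper or lower GI symptom (section 1).
- Per cohort: 25 × (1 − 0.60) = 10. Over both: 50 × 0.40 = 20.
- Because 60% is the top of the quoted range, 20 is about the minimum on that figure. Diarrhoea cannot be more common than any GI symptom. Shares p of 60%, 40% and 20% are used below; the last two are assumptions.

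**2. Chance that a cohort's placebo arm has no patient with diarrhoea.** Formula: (1 − p)^n.
- n = 5 (20 BSS and 5 placebo, section 3.5.2): 0.4^5 = 1%; 0.6^5 = 8%; 0.8^5 = 33%. The expected number with diarrhoea is 3, 2 or 1.
- n = 12 (a fair coin toss, section 3.5.1, giving about half of 25): 0.4^12 ≈ 0%; 0.6^12 = 0.2%; 0.8^12 = 7%.

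**3. Effect divided by its standard error.** Assumptions: patients with diarrhoea average 5 stools/day (SD 2) and BSS lowers this by 1.5; others average 1.5/day (SD 0.7) with no effect; the cohorts are pooled at 40:10; variance is equal in the two arms.
- Sample-size factor: √(40 × 10 / 50) = √8 = 2.83.
- Mean effect in all patients: 1.5p = 0.9, 0.6 or 0.3.
- Within-group variance: W = 4p + 0.49(1 − p) = 2.596, 1.894 or 1.192.
- Between-group variance: B = p(1 − p) × 3.5² = 2.94, 2.94 or 1.96.
- All patients, unadjusted: 1.5p × 2.83 / √(W + B).
- All patients, adjusted for baseline diarrhoea status: 1.5p × 2.83 / √W.
- Diarrhoea stratum only: (1.5 / 2) × √(8p).

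| Share with diarrhoea | Unadjusted | Adjusted | Stratum only |
|---|---|---|---|
| 60% | 1.08 | 1.58 | 1.64 |
| 40% | 0.77 | 1.23 | 1.34 |
| 20% | 0.48 | 0.78 | 0.95 |

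Adjustment raises the ratio by about 46%, 60% and 63%. Restricting to the stratum then adds about 4%, 9% and 22%.

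**4. Sensitivity.**
- If the other patients have an effect of only 0.1 stools/day, the mean effect becomes 1.5p + 0.1(1 − p) = 0.94, 0.66 or 0.38. The adjusted ratio becomes 1.65, 1.36 or 0.98, and the stratum's lead disappears.
- At 25:25 the factor is √12.5 = 3.54. Every ratio in the table rises by 1.25 and the ranking is unchanged.

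**The case against.** The strongest reply is that the trial is a proof-of-concept pilot in mild to moderate COVID-19. It also looks at tolerance and at the gut as a viral reservoir. Those aims call for a test-positive population, and the entry criteria match the objective as written. This stands. A reader might infer that the trial cannot answer its primary question, or that diarrhoea must become an entry criterion. The documents support neither: the question is diluted rather than unanswerable, and narrowing entry is a trade-off against the other aims and against recruitment.

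A second reply is that section 2 also speaks of change in stool frequency, and a change-from-baseline analysis would recover much of the lost precision. That is right in substance, and it is why most of the shortfall comes from ignoring baseline rather than from eligibility. But no section specifies such an analysis.

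A reader might also infer that patients with normal counts have nothing to decrease, or that BSS would produce constipation that passes for efficacy. A normal count can still fall, and no section gives a constipation rate for BSS. What holds is narrower: the endpoint cannot tell such a fall from relief of diarrhoea. Dilution with zero effect in those patients and a fall in those same patients are alternative scenarios, not simultaneous ones.

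The exclusion of anti-diarrhoeal drugs is no fault. It protects the endpoint from confounding and removes users of those drugs, not patients with diarrhoea as such.

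Finally, section 3.6.1 names negative saliva rates as the primary efficacy analysis. Whether stool frequency is primary is itself unsettled, and that conflict comes first.

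**Conclusion.** The concern holds as a should-fix. It is certain from the text that no entry criterion concerns bowel habit, and that the plan gives the baseline stool count no role in allocation or analysis. On the protocol's own upper figure, about 20 or more of 50 randomised patients would be expected to have no GI symptom, provided the trial population resembles the studies the background refers to.

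The size of the loss is illustrative. It rests on the assumed diarrhoea share, means, SDs and 1.5-stool effect, and on pooling two cohorts that section 3.1 describes as separate studies. The risk of a placebo arm without diarrhoea depends heavily on which allocation statement governs: 1%, 8% or 33% per cohort at 20:5, but about 0%, 0.2% or 7% with a fair coin. The durable result is that using baseline gives most of the gain. Restricting the primary analysis adds little, and only if the other patients show no effect.

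**What to change.** First reconcile which endpoint is primary (section 2 versus section 3.6.1) and the allocation ratio (the coin toss in section 3.5.1 versus 20 and 5 in section 3.5.2). Then:

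1. Stratify allocation within each randomised cohort by baseline stool frequency, for example 3 or more per day versus fewer, using the screening count. Tossing a coin separately in each stratum would balance nothing, so this needs a blocked list per stratum. Section 3.5.1 already allows a method other than the coin.
2. Adjust the stool-frequency comparison for baseline stool frequency.
3. Prespecify the comparison in patients with a raised baseline count and report it beside the all-randomised result, so that a fall in patients with normal counts is not read as anti-diarrhoeal efficacy.

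The cost is protocol and SAP wording plus one allocation stratum. No extra patients are needed, and a cut-off based on frequency needs no new data. A definition based on loose or watery stools would need a consistency item, because the documents do not describe what the symptom questionnaire contains. The downside is a small subgroup: at 20:5, about 3, 2 or 1 placebo patients per cohort would have diarrhoea at shares of 60%, 40% or 20%, so that estimate will be imprecise. Making diarrhoea an entry criterion for the randomised cohorts would avoid this at the price of slower recruitment. It is an option for the sponsor, not a requirement.

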3.3 Removal of Patients from the Study

During the study, patients will be withdrawn if any of the following applies:

- · Patient's request;
- Complicated COVID-19 infection that requires intubation;
- The Investigator determines that continued participation may cause harm. The Investigator always has the right to withdraw patients in the event of adverse events (AEs), intercurrent illnesses, protocol violations, laboratory abnormalities, treatment failure, or for administrative or other reasons:
- The patient becomes pregnant the treatment code will be revealed and the patient will be referred to an obstetrician and followed throughout the remainder of the study period

When possible, any patient who is withdrawn from the study during the treatment period will undergo all end-of-treatment (Day 21) procedures at the time of withdrawal, regardless of the length of treatment s/he received. Patients withdrawn from the study for medical reasons will remain under medical supervision until the Investigator deems the condition to be resolved or stabilized.

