3.4.1.3 Daily Visits (1+/-21 Days)

The visits may occur daily up to Day 21(whichever comes first), or until the patient tests COVID- by saliva test. The following procedures will be performed at this visit:

- a. Medication history updated to include any changes or new medications since baseline;
- b. Recording of daily stool frequency and symptom questionnaire;
- c. Patient daily testing by saliva sample for COVID-19
- d. Assessment of AEs;
- e. Stool specimen collection at Day 7, Day 14 and Day 21. Collection kits to be given to patient 1 day prior if in an outpatient setting.

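### The one-of list for women in Section 3.2.1 can be read so that contraception is bypassed, and the section it cites to define contraception does not exist

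*Combined protocol and SAP*

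**What the plan says.** Section 3.2.1 introduces the criteria for women with "Women should fulfill one of the following criteria". Four items follow in the printed text:

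1. an affirmative answer that "they are not or could not be pregnant";
2. post-menopausal status;
3. surgical sterility;
4. for women of childbearing potential in heterosexual relations, that they "must be willing to use adequate contraception from Screening through the 21 Day visit, per Section 10.2".

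Four other places bear on pregnancy:

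- Section 3.2.2 excludes current pregnancy, breast-feeding and any plan to conceive during the trial.
- Section 3.4.1.1, item h, takes a verbal not-pregnant statement at screening.
- Section 3.3 lists among the grounds for withdrawal: "The patient becomes pregnant the treatment code will be revealed and the patient will be referred to an obstetrician".
- The Appendix 1 schedule has no row for contraception.

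The numbered sections of the protocol run from 1 to 5. Section 5 is the appendices, which are numbered 1 to 3.

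**The concern.** The rule joining the four items asks for any one of them. The first is a statement that almost every eligible woman can make. If it is enough on its own, the fourth item never has to be met. The woman for whom contraception matters most, who is fertile, sexually active and not pregnant at entry, would then qualify without it.

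The protocol plainly wants such women to use contraception: it says so in item 4, excludes pregnancy, and unblinds and refers any patient who conceives. A criterion that staff can apply in a way that defeats that aim is a weakness in patient protection. Women of childbearing age are plausible recruits, since entry starts at age 18 and Section 3.1 names a campus health service, including its students, as a recruitment source.

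A second weakness sits in the same item. The standard that a woman must meet is delegated to a section that is not in the document, so two members of staff could apply different standards.

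**Working it through.** No arithmetic applies, and the plan gives no figure to reproduce. The check is one of logic and cross-reference.

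**Step 1: the list as an either-or rule.** Write N for the not-pregnant statement, M for post-menopausal, S for sterile and C for contraception. The printed rule is N or M or S or C. Section 3.2.2 has already removed pregnant women, so nearly every woman still eligible can truthfully give N. The rule then reduces to N, and M, S and C do no work.

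| Woman, not pregnant at entry | N | M or S | C | Printed rule, read literally | Contraception mandatory |
|---|---|---|---|---|---|
| Post-menopausal or sterile | yes | yes | not applicable | eligible | eligible |
| Fertile, in heterosexual relations, agrees to contraception | yes | no | yes | eligible | eligible |
| Fertile, in heterosexual relations, does not agree | yes | no | no | **eligible** | **not eligible** |
| Fertile, not in heterosexual relations | yes | no | not applicable | eligible | eligible |

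The two readings differ only in the third row.

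**Step 2: does another section close that row?**

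- Section 3.2.2 deals with pregnancy at entry and intended pregnancy. It is silent on unintended conception.
- Section 3.4.1.1, item h, records status on one day.
- Section 3.3 acts only after conception.
- Neither the screening list nor Appendix 1 prompts staff to ask about contraception.

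None of these requires contraception. Item 4 of Section 3.2.1 is the only text that does.

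**Step 3: the cross-reference.** Item 4 points to Section 10.2. The body stops at Section 5, and the visible contents entries pass from Section 4.2 to the appendices. This does not look like redaction or a removed page. Other references are also out of step: Section 3.5.5 cites Section 3.4 for patient removal, which is in Section 3.3, and Section 3.4.1 places the schedule in Appendix 2 although it is Appendix 1. A reference left over from another numbering is the likely explanation. The effect is that no visible text defines adequate contraception.

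**The case against.** The strongest reply is that the layout has been lost. In the extracted text the women's criteria appear to fall under the definition of COVID infection, and the lead-in line sits level with its own items. Indentation therefore cannot show where the one-of list ends. The wording also favours a separate criterion: items 2 and 3 are short status phrases, whereas item 4 is a full sentence stating an obligation for a named subgroup. This stands. A reader might infer that the protocol waives contraception for women who say they are not pregnant. The documents do not support that; they support only that the printed list permits such a reading.

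The missing screening entry is weak evidence by itself. Section 3.4.1.1 also omits the ability to chew tablets, menopausal status and sterility, so it is not a full eligibility checklist. Consent pages are not available, so what women are told there is unknown.

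A reader might also infer that the contraception period has no usable end, because visits can stop early ("or until the patient tests COVID- by saliva test") and withdrawn patients "will undergo all end-of-treatment (Day 21) procedures at the time of withdrawal". That goes too far. Item 4 states a limit, and continuing to Day 21 after an early stop is conservative. No change to the end date is needed.

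What survives the reply is that the criterion is open to misapplication and that its definition is missing.

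**Conclusion.** The point holds as a minor patient-protection correction. Read literally, Section 3.2.1 lets a fertile, sexually active woman who is not pregnant enrol without agreeing to contraception, although the obligatory wording of item 4 suggests that this was not meant. The undefined standard holds on either reading.

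The size is small. Pregnancy at entry, intended pregnancy and pregnancy occurring on study are already covered. What remains is unintended conception around a course of at most 21 days in the blinded groups and 3 days in the open-label group. The documents give no proportion of women, fertility rate or pregnancy rate, so no number of affected patients is claimed. It could be none, if staff treat item 4 as mandatory. There is no effect on power, error rates or endpoints, and nothing here calls the trial's results into question.

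The conclusion assumes that the four items appear in the source in the printed order under the one-of lead-in, and that no Section 10 exists in the full protocol.

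**What to change.** Reword the criterion along these lines:

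> Every woman must affirm that she is not pregnant AND must be one of: (a) post-menopausal; (b) surgically sterile; or (c) of childbearing potential and, if in heterosexual relations, willing to use adequate contraception from Screening through Day 21.

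Keep the existing definitions of post-menopausal and surgically sterile. Replace the reference to Section 10.2 with a list of acceptable methods in the text, confirmed by the investigator and the IRB. Record the agreement on the screening form beside item h of Section 3.4.1.1.

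The cost is the wording of one criterion, a short list of methods and one line on a form, all of which can go into the next amendment. No test, visit or patient is added. The downside is that a few women unwilling to use contraception would not be enrolled.
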